### 3.4 Lost Restorations

For any restoration that is lost during the 24-months of follow-up, an offer will be made to replace the restoration using normal IUSD techniques and materials at no charge.

#### **4.0 Statistical Considerations**

The two techniques will be compared for differences in sensitivity, retention, marginal discoloration, marginal adaptation, and clinical acceptability at each follow-up visit using Cochran-Mantel-Haenszel tests for stratified, ordered categorical outcomes. The study subjects are considered the 'strata' in this method so that the comparisons properly account for the use of both techniques in each subject. This method also easily extends to having multiple teeth receiving each technique for each patient.

With a final sample size of 30 subjects, the study will have 80% power to detect a 35% difference between the two treatment methods, assuming two-sided tests of paired proportions and a 5% significance level. To account for attrition the study will enroll 33 subjects.

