## Appendix G-3

Indiana University School of Dentistry  
 Graduate Student Research Proposal Abstract Form  
 (for review by the IUSD Research Subcommittee)

Project Title: Clinical Evaluation of a Universal Adhesive in Non-Carious Cervical Lesions

Name

Signature\*\*

Principal Investigator:	[name]	
Co-investigator (student):	[name]	
Research Committee:	[name]	
	[name]	
	[name]	
	[name]	

Project Biometrist: [name]

Department/Program: Operative / Preventive

Cost of Project: \$40,532 Dates of Project: Feb 2014 - May 2016

Use of: Human Subjects or Tissues: ✓ Animals: \_\_\_\_\_ Biohazards or rDNA: \_\_\_\_\_

Reviewed by [name] (IRB, only if human subjects involved) ✓

Reviewed by [name] (Good Clinical Practice, only if human subjects involved) \_\_\_\_\_

Reviewed by [name] (Research Billing Compliance, only if human subjects involved) \_\_\_\_\_

\*\*Signature indicates that the proposal has been read and approved.

Place Abstract on separate page and attach prior to remainder of proposal.

Clinical Evaluation of a Universal Adhesive in Non-Carious Cervical Lesions

Background/Relevance: For decades, resin adhesives have been used to restore non-carious cervical lesions for esthetics and/or patient comfort. New “universal adhesives” claim to simplify the process of bonding resin composites to tooth structure while maintaining or exceeding the quality of previous adhesive systems. Since dentin and enamel substrates are vastly different with respect to composition and therefore require different bonding protocols, some have advocated a “selective etch” procedure in which the enamel and dentin are etched differently but may still be bonded using a similar bonding agent. The purpose of this study is to determine whether or not a selective etch protocol used with a universal adhesive provides significantly improved results in comparison to a self-etch protocol when restoring non-carious cervical lesions.

Rationale: In vitro studies have shown statistically significantly superior marginal adaptation and color stability with a selective etch technique, but there are currently no prospective in vivo studies greater than 6 months comparing the efficacy of selective vs. self- etch techniques in conjunction with a universal adhesive.

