Methods: Thirty-three patients with at least two non-carious cervical lesions (NCCLs) will receive one restoration utilizing the self-etch universal adhesive (Adhese Universal, Ivoclar Vivadent) with no separate enamel etching and another restoration utilizing the universal adhesive and a selective etch protocol in which enamel is etched with 37% phosphoric acid. The adhesive and Tetric composite will be provided by Ivoclar and manufacturer’s instructions will be followed for placement of the restorations.

Alternate Hypothesis: Selective-etch restorations will show superior retention rates, marginal adaptation, and color stability after 2 years compared to self-etch restorations.

Relevance: With so many different types of resin adhesives and numerous proposed methods, this study could provide evidence supporting one protocol and eliminate some of the confusion associated with resin bonding protocols.

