### **Purpose/Specific Aims:**

The purpose of this prospective clinical trial will be to evaluate the efficacy of a newly formulated “universal” dental adhesive formulation in adult noncarious cervical lesions using self-etch and selective etch approaches; the aim is to determine whether or not selective etching provides significantly improved retention and/or better resistance to enamel margin discoloration in comparison to self-etching over a 24 month period.

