### **Hypothesis:**

The alternate hypothesis is that the restorations placed utilizing a selective etch method will yield superior retention, marginal adaptation, and less marginal discoloration than restorations placed with the self-etch method.

The null hypothesis is that there will be no significant differences with respect to retention, marginal adaptation, or marginal discoloration when comparing restorations placed with selective etch and self-etch methods.

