#### **5.0 Investigator Responsibilities and Regulatory Requirements**

This study will be conducted in accordance with the applicable GCPs, 21 Code of Federal Regulations (CFR) 50, 56, and 312; International Conference on Harmonization (ICH) Good Clinical Practice published in the Federal Register: 9-May-97 (volume 62, number 90), pages 25691–25709.

The Principal Investigator will perform or directly supervise the performance of all the study procedures in accordance to the highest standards of medical and clinical research practice. Delegation of any study responsibility will be documented in writing. The Investigator and Student Investigator will follow the protocol as written and to ensure that all members of the assisting staff also understand and follow the protocol. If

[name]

changes to the protocol are needed, an IRB approved amendment will be gained prior to initiation of any new or changed procedures.

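### Section 4.0 names no primary outcome, visit or decision rule, and the aim and hypothesis imply different ones, so the 5% level covers no overall superiority claim and the 80% power belongs to one unnamed comparison.

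*Combined protocol and SAP*

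**What the plan says.** Section 4.0 (Statistical Considerations) plans Cochran-Mantel-Haenszel tests, stratified by subject, of "sensitivity, retention, marginal discoloration, marginal adaptation, and clinical acceptability at each follow-up visit". Section 3.3 sets the visits at about 6, 12 and 24 months. The power statement is a single sentence: with 30 subjects, "the study will have 80% power to detect a 35% difference between the two treatment methods, assuming two-sided tests of paired proportions", at a 5% significance level. It does not say which outcome or visit the 35% refers to, or what proportion of pairs is expected to be discordant. Section 4.0 designates no primary outcome or visit, gives no rule for combining outcomes and makes no multiplicity adjustment. No other section supplies these.

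The research question is worded in four places:

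- Purpose/Specific Aims, two outcomes: "significantly improved retention and/or better resistance to enamel margin discoloration in comparison to self-etching over a 24 month period".
- Hypothesis, alternate, three outcomes: selective etch "will yield superior retention, marginal adaptation, and less marginal discoloration than restorations placed with the self-etch method".
- Hypothesis, null, the same three: "no significant differences with respect to retention, marginal adaptation, or marginal discoloration".
- Appendix G-3 abstract, three outcomes: "superior retention rates, marginal adaptation, and color stability after 2 years compared to self-etch restorations".

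The aim and the abstract point to 24 months. Section 4.0 does not turn that into a primary analysis.

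**The concern.** Suppose that at 24 months only marginal discoloration differs significantly, in favour of selective etch. The aim is met, because either of its outcomes is enough. The null as worded is rejected, because one of its three outcomes differs. The alternate as worded is not established, because it lists three outcomes joined by *and*. The null and the alternate are not complements, so the Hypothesis section does not settle the matter by itself.

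The deciding result can therefore be chosen after the data are seen. The two stated operating figures also fail under different rules. Accepting any one outcome raises the false-positive rate above 5%. Requiring all outcomes leaves the error alone but lowers the chance of success. If each outcome is judged separately, 5% applies to each of them, and no overall claim that selective etching is superior is covered.

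**Working it through.** **Inputs.** From section 4.0: n = 30 pairs, difference d = 0.35, two-sided α = 0.05, power 0.80. From Hypothesis: three outcomes. From Purpose/Specific Aims: two outcomes. The discordant proportion ψ and the correlation between tests are not in the documents. They are assumptions here and are varied.

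**1. The plan's own 80%.** The normal approximation for paired proportions is

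Power = Φ[(√n·d − z·√ψ) / √(ψ − d²)], with z = 1.960 for two-sided 5%.

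With n = 30 and d = 0.35, √n·d = 1.917 and d² = 0.1225. At ψ = 0.507: (1.917 − 1.960 × 0.712) / √0.3845 = 0.521 / 0.620 = 0.841, and Φ(0.841) = 0.80. Other values of ψ give:

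| ψ | 0.35 | 0.40 | 0.45 | 0.50 | 0.55 | 0.60 | 0.65 |
|---|---|---|---|---|---|---|---|
| Power | 94% | 90% | 85% | 81% | 76% | 72% | 68% |

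The 80% is thus attainable for one paired comparison but cannot be reproduced from the stated inputs alone. By enumeration, the value of ψ that gives 80% is 0.467 for the exact McNemar test and 0.532 for the uncorrected one.

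**2. Any one of k outcomes suffices, at 24 months only.** For independent tests the false-positive rate is 1 − (1 − 0.05)^k:

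- k = 3: 1 − 0.95³ = 14.3%
- k = 2 (the aim): 1 − 0.95² = 9.75%

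The bound under any dependence is k × 0.05, so 15% for three outcomes and 10% for two. With equicorrelated normal test statistics, by numerical integration:

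| Correlation | 0 | 0.3 | 0.5 | 0.8 | 0.9 |
|---|---|---|---|---|---|
| Any of 3 | 14.3% | 13.6% | 12.5% | 9.8% | 8.4% |

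These are nominal rates. If few pairs are discordant, a 5% test on 30 pairs rejects less often than 5%. Enumerating the uncorrected McNemar test, which equals CMH for binary pairs, gives true sizes of 0.65%, 3.1% and 4.7% at ψ = 0.05, 0.10 and 0.15. For three independent tests, 1 − (1 − size)³ is then 1.9%, 8.9% and 13.3%. This is a guide only, because the planned CMH test uses three-level ratings and allows a third tooth.

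**3. All three required.** The error of the joint claim is at most 5%. Joint power cannot exceed the power of the weakest single test. As an illustration only, let each test have 80% power on 30 rated pairs. Joint power is then 0.8³ = 51% if independent, 61% at correlation 0.5, and 80% only at correlation 1.

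**4. Price of Holm.** The strictest step for three outcomes is α = 0.05/3 = 0.0167, with z = 2.394. At ψ = 0.507: (1.917 − 2.394 × 0.712) / 0.620 = 0.343, and Φ(0.343) = 63%.

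**The case against.** The strongest reply is that the connecting words are being over-read. The aim, alternate and null may simply list endpoints, each compared on its own. Section 4.0 fits that reading: it compares the techniques outcome by outcome and powers on tests in the plural. The plan nowhere claims a familywise error rate or a joint power. This stands in part. Separate comparisons are a legitimate reading, and under it nothing is inflated. But the plan does not say that this is the intent, and that reading supports no overall superiority statement.

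A second objection also stands. The joint-power figures assume 30 rated pairs and an equal 35-point effect on every outcome. Under the criteria in section 3.3, a completely lost restoration has no margin to rate, and no section says how it would be scored. A large retention effect through complete loss would leave fewer pairs for the two margin outcomes. The 51% and 61% therefore show direction and are not forecasts.

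A reader might go further in three ways that the documents do not support:

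- **Five outcomes at three visits give an error near 54%** (1 − 0.95^15). That treats all 15 comparisons as independent routes to the claim, while the aim and hypothesis confine it to two or three outcomes and the aim and abstract point to 24 months.
- **The 80% is wrong.** It is under-specified, and a discordant proportion near 0.51 would produce it.
- **Naming retention as primary preserves 80% power.** No section gives an expected retention rate or discordance from which to judge that.

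**Conclusion.** The point holds as a gap in the decision rule. It does not show that the plan's arithmetic is wrong. As written, the plan does not say which 24-month result decides the question, and its wording allows at least three rules. An any-of-three claim carries a nominal error of about 14% under independence, falling to 8.4% at an assumed correlation of 0.9, and lower still with sparse ratings. An all-of-three claim holds the error but has less power than any single test unless the tests are perfectly correlated. The stated 80% is for one unnamed paired comparison and runs from about 94% to 68% over discordance 0.35 to 0.65. The conclusion that a rule is missing rests on the text alone. The sizes rest on assumed correlations and discordance. The trial remains analysable, so this should be corrected but does not invalidate the design.

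**What to change.** In section 4.0, make 24 months the primary time point and adopt one of two rules:

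- The investigators name one primary outcome, tested at two-sided 5%. Retention and marginal discoloration are both in the aim and the hypothesis, so either is a candidate.
- The three hypothesis outcomes stay primary under Holm's procedure at an overall two-sided 5%, and only those that pass are claimed.

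Make all other outcomes and the 6- and 12-month comparisons secondary, reported as paired differences with 95% confidence intervals. Reword the aim and the hypothesis to match the chosen rule. Restate the power sentence to name the outcome, the visit and the assumed discordant proportion, and to say that the power is for a single test.

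The cost is a paragraph in section 4.0 and matching wording elsewhere, with no extra patients or data. Section 5.0 supplies the route: "an IRB approved amendment will be gained prior to initiation of any new or changed procedures". The amendment should be dated and state whether outcome data had been seen, since the abstract form gives "Dates of Project: Feb 2014 - May 2016" and amendment 4 was created on 02/16/2015. The downside of a single primary outcome is a narrower primary claim. The downside of Holm is about 63% power for a given outcome at its strictest step, at the discordance of about 0.51 where a single 5% test has 80%.

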#### **5.0 Investigator Responsibilities and Regulatory Requirements**

This study will be conducted in accordance with the applicable GCPs, 21 Code of Federal Regulations (CFR) 50, 56, and 312; International Conference on Harmonization (ICH) Good Clinical Practice published in the Federal Register: 9-May-97 (volume 62, number 90), pages 25691–25709.

The Principal Investigator will perform or directly supervise the performance of all the study procedures in accordance to the highest standards of medical and clinical research practice. Delegation of any study responsibility will be documented in writing. The Investigator and Student Investigator will follow the protocol as written and to ensure that all members of the assisting staff also understand and follow the protocol. If

[name]

changes to the protocol are needed, an IRB approved amendment will be gained prior to initiation of any new or changed procedures.

### **5.1 Advertising**

Advertisements including brochures and telephone interview text for subject recruitment will be approved by the IRB prior to study initiation.

### **5.3 Subject Consent**

Written informed consent will be obtained from also subjects prior to their participation in any research procedure. This consent form will comply with all applicable regulations governing the protection of human subjects. The elements of informed consent and the documentation of informed consent will follow specifications in 21 CFR 50.25 and 50.27 and/or ICH GCPs chapter 4.

Each subject will sign and date an informed consent prior to participation in the study. A signed copy of the consent form will be given to the subject and the original will be retained by the Investigator. Subjects may withdraw from participation in the study at any time. Additionally, the Investigator may withdraw subjects from the study if it is in the best interest of the subjects. The reason for all subject withdrawals from the study will be documented on the appropriate CRF.

## **5.4 Data Collection**

The Investigator will ensure that all source documents (i.e., study and/or medical records) and Case Report Forms (CRFs) are completed and maintained according to the study protocol.

### **5.4.1. Case Report Forms**

The Investigator will supply the paper and/or electronic CRFs to be used in this study. It is the responsibility of the Investigator to maintain accurate CRFs. All hard copy CRFs will be filled out legibly in ink.

For paper CRFs, if an entry requires correction, a single line will be placed through the entry so as not to obscure the original record, the corrected entry will be initialed and dated by the individual making the change. There will be no whiteouts or erasures. For electronic CRFs, if an entry requires correction, the change is made directly to the CRF in the database, the user is prompted to provide a reason for the change, and the correction is logged in by an electronic audit trail. If, for any reason, the subject does

[name]

not complete the study, an explanation will be entered on the Subject Accountability CRF.

#### **5.4.2. Source Documents**

All source documents (i.e., study and/or medical records) and CRFs will be completed and maintained according to the study protocol. Any CRF used as a source document must be identified as such in the Investigator's Study Notebook.

### **5.5 Study Device Dispensing, Storage, and Accounting**

The study device to be used in this study will be supplied by Ivoclar. Upon receipt of the study devices, the Investigator will store them in a secured area. Records of all study devices will be maintained by the Investigator's staff using a Device Dispensing Record. The dispensing of the study devices will be under the Investigator's supervision, and only administered to those subjects who meet the entry criteria.

### **5.6 Adherence to Protocol**

The Investigator will adhere strictly to the protocol (See Section 3.7 for preparing protocol amendments). The Investigator will ensure that all protocol deviations are documented, as they occur, in the Investigator's Study Notebook.

### **5.7 Adverse Event Reporting**

Any adverse events spontaneously expressed by the panelists or observed by the Study Dentist or Investigator will be recorded giving full details including: date of onset, duration, severity, treatment given, final resolution, and will include the investigator's assessments. The Investigator will determine the need for further examination. Should

a serious adverse event occur, the Investigator will instruct the subject to report back to the study site at appropriate intervals until remission has occurred. All such visits will be documented. The Investigator will prepare a written statement describing the serious adverse event and the medical management of the adverse event. All Adverse Events will be reported to the IRB in the annual report. Serious Adverse Events that are directly related to the study will require IRB notification within 3 working days. A serious event is defined as an event that suggests a definite hazard or handicap to the subject. Serious events are any events resulting in death, decreased life expectancy, life-threatening situation, permanent disability, hospitalization, drug overdose with study medication, or congenital anomaly.

## **5.8 Records Retention**

Study records will be stored for a minimum of 7 years after the last regulatory approval has been received or the discontinuation of the study. Study records will be made available for inspection and copying upon the request of authorized personnel.

**Budget:**

Anticipated Start Date: February 1, 2013

Requested from Research Committee			Supplied "in kind" from Other Sources		
Category	Description	Amount	Description	Amount	Source
Personnel:		\$ 0	Calibrators, Evaluators, Assistant	\$ 28,762	Ivoclar Vivadent
Equipment:		\$ 0	Clinical equipment	\$ 750	Ivoclar Vivadent
Supplies:		\$ 0	Adhesive, composite	\$ 3,000	Ivoclar Vivadent
Panelist Payments		\$ 0		\$	
Bio-statistics		\$ 0	Statistical analysis	\$ 320	IUSD
Other		\$ 0	Patient Incentives, IRB Fee	\$ 7,700	Ivoclar Vivadent
			Cost of Procedures	\$ 3,201	Ivoclar Vivadent
Total Requested from		\$ 0	Total of funds provided		\$ 43,733

[name]

Research Committee		from other sources:	
Total Cost of Proposed Project: \$ 43,733
